#### 4. Abstract

Title	Sepsis-Associated Purpura Fulminans International Registry - Europe
Short title (Acronym)	SAPFIRE
Rationale and background	
Purpura fulminans is the clinical manifestation of disseminated thrombosis in dermal and systemic microcirculation. This rare disease is frequently associated with multiple organ failure and represents a life-threatening condition with mortality exceeding 50 %. Apart from isolated idiopathic cases, deficiency of Protein C, a major intrinsic anti-coagulant, is considered the leading cause of Purpura fulminans. In the vast proportion of cases, the condition has been shown to emerge secondary to acquired Protein C deficiency associated with severe sepsis, mostly of meningococcal or pneumococcal origin.
 
A consistent therapeutic approach to sepsis-associated Purpura fulminans (SAPF) has not been established yet. With exaggerated pro-coagulant activity being confirmed as the key pathogenic aspect, several treatment modalities aiming at the balance restoration in the coagulation cascade have been considered. Based on the experience gathered in patients with inherited Protein C deficiency, supplementation with Protein C formulations has been used as adjuvant therapy in SAPF.
 
Most of the information on SAPF incidence and therapy has been obtained before 2004. Meanwhile, lack of comprehensive data poses considerable difficulties with regard to its diagnosis and treatment. SAPF causality might have been substantially altered in the wake of widespread meningococcal vaccination. There are neither evidence-based treatment guidelines nor comparative evaluation of the efficacy of different therapeutic approaches. Therefore there is a pronounced need of systematic data collection and evaluation covering several aspects of SAPF, such as epidemiology, causality, morbidity and therapy.

Research question and objectives	
 
Systematic acquisition, analysis and dissemination of information on incidence and prehospital/inhospital course of Purpura fulminans, (possible long-term follow up) and its relation to infectious agents (e.g. meningococcemia, streptococcus etc.)
 
Systematic acquisition, analysis and dissemination of information on current management of PF (sepsis bundles and replacement strategies – protein C, AT, etc.)
 
Systematic acquisition, analysis and dissemination of information on outcomes (morbidity, mortality) of PF with current management strategies, stratified for use or non-use of protein C
 

Design	Prospective multicenter registry derived from systematic data collection on the incidence and treatment of sepsis-associated Purpura fulminans
Population	Patients diagnosed with Purpura fulminans associated with severe sepsis

Endpoints	
 
• All-cause in-hospital mortality
 
• Morbidity at defined post-diagnosis intervals and over 7 consecutive days 
 
- Mean total SOFA score (age <math>\geq 16</math>)
 
- PELOD score (age <math>< 16</math>)
 
- <math>\Delta</math>SOFA or dPELOD score for day-to-day comparisons
 
 
 
• Extent and severity of Purpura lesions
 
• Need for reconstructive surgery (amputations, skin grafts)
 
• Length of ICU stay (days)
 
• Length of hospital stay (days)
 
• Changes in hematological parameters 
 
- WBC count
 
- Thrombocyte count
 
- Hemoglobin
 
 
 
• Changes in coagulation parameters 
 
- Prothrombin time (PT)
 
- Activated partial thromboplastin time (aPTT)
 
- Fibrinogen
 
- D-dimers
 
- Thrombin-antithrombin complex (TATc)
 
- Protein C activity
 
- Antithrombin III activity
 
 
 
• Changes in inflammatory parameters 
 
- C-reactive protein (CRP)
 
- Procalcitonin (PCT)
 
- Interleukin 6 (IL-6)
 
 
 
• Changes in organ dysfunction parameters 
 
- Glucose
 
- Lactate
 
- Creatine kinase (CK)
 
 
 
• Duration of mechanical ventilation (days)
 
• Duration of renal replacement therapy (days)
 
• Vasopressor use (days/doses)
 
• Sepsis-inducing pathogen
 
• Adverse event related to PF treatment (reporting as per decision of the investigator) 
 
- Bleeding
 
- Thrombotic events
 
 
 

Inclusion criteria	
 
- Diagnosis of severe sepsis and Purpura fulminans
 
- Signed informed consent (according to local legal regulations)
 

Exclusion criteria	
 
- premature neonates (<math>< 36</math> gestational week)
 

Centers	Approx. 30 participating centers in Germany, Austria, Ireland, UK, Italy, Spain, Netherlands (selected centers)

Timetable	First patient in	Q3 2015
	Registry duration	3 years, with an option of prolongation
	Estimated enrolment	Approx. 50 patients/year
	Interim Analysis	Biannually

## 5. Amendments and updates

Number	Date	Section of registry protocol	Amendment or update	Reason
01	30.9.2015		Update	
 
• Flowchart optimization
 
• Staff change
 
• ADR reporting
 

02	31.08.2017		Update	
 
• 
 

03	11.07.2019		Update	
 
• Staff change
 
• Milestones delete
 

## 6. Rationale and background

*Purpura fulminans* is a life-threatening and highly disabling condition characterized by rapidly evolving thrombosis in the dermal and systemic microcirculation. The estimated incidence of the disease is 0.1 per 100,000 inhabitants [Nicolas and Debonne, 2002]. It is associated with high mortality (above 50 %), owing to progressive cutaneous hemorrhage and multiple organ dysfunction. Profound tissue lesions and grave disturbance in numerous vital functions also determine a considerable long-term morbidity and disability.

Apart from a few cases of idiopathic origin, the etiology of *Purpura fulminans* is ascribed to either congenital abnormality or acquired deficiency of Protein C-operating anticoagulant pathways. The latter condition is in the vast majority secondary to an acute severe infection, thus coining the term sepsis-induced or sepsis-associated *Purpura fulminans* (SAPF) [Betrosian et al., 2006]. Several bacterial pathogens can induce SAPF, with meningococcal and pneumococcal infections accounting for the majority of cases. Causal involvement of viral and protozoan pathogens also has been described [Betrosian et al., 2006].

The pathogenesis of SAPF exemplifies the induction of a coagulopathy by the intertwined action of extrinsic bacterial (e.g. endotoxins) and intrinsic (e.g. vascular, inflammatory and hematologic) factors. The decay of endogenous anti-coagulant systems has a decisive contribution to the imbalance of clotting in sepsis and the presence of a consumptive coagulopathy is a distinct feature of infection-associated *Purpura fulminans* [Darmstadt, 1998]. Extensive similarities with clinical and pathological characteristics of *Purpura fulminans* in congenital Protein C deficiency have brought this endogenous anti-coagulant into focus with regard to the pathogenesis of SAPF [Francis, 1990]. Indeed, SAPF reflects an exaggerated pro-coagulant response resulting from decreased abundance/activity of endogenous anticoagulants, such as antithrombin and Protein C [Dempfle,

2004]. Meanwhile, ample evidence has accumulated in support of the view that circulating Protein C concentrations markedly decline in severe sepsis, due to both, suppressed biosynthesis and increased consumption/degradation [Fourrier et al., 1992; Leclerc et al., 1992; Borgel et al., 2006; Shorr et al., 2006].

The emergence of SAPF lesions is considered a localized manifestation of the Shwartzman phenomenon [Francis, 1990]. Bacterial endotoxin-triggered endothelial damage, inflammatory cytokine release and tissue factor production, in conjunction with continuous thrombin generation and breakdown of the regulatory feedback exerted by natural anti-coagulants, lead to multiple intravascular coagulation, perivascular infiltration and extravasation, which become manifest as cutaneous lesions. The latter evolve rapidly from scattered erythema to petechiae and ecchymoses, and ultimately to necrosis of the skin and subcutaneous tissue. As intravascular coagulation occurs simultaneously in visceral organs as well, signs of multiple organ dysfunction and failure are integral parts of the clinical presentation [Francis, 1990].

Although several therapeutic interventions have been employed in the past, currently there are no evidence-based medical management guidelines for SAPF. Pathogenesis-targeting approaches generally aim at the restoration of balance of pro- and anti-coagulation pathways, thereby curtailing intravascular clotting. The broad array of such disease-modifying options [Darmstadt, 1998] has been narrowed over time to the supplementation of essential endogenous anti-coagulants as either whole plasma products (fresh frozen plasma, cryoprecipitate, and plasmapheresis) or single-protein formulations (Protein C concentrate, recombinant activated Protein C, antithrombin III, tissue plasminogen activator). The therapeutic experience with these products has been described in several studies [Cobcroft et al., 1994; Ettinghausen et al., 1999; Rintala et al., 2000; White et al., 2000; de Kleijn et al., 2003; Dhainaut et al., 2004; Zenz et al., 2004; Vincent et al., 2005; Schellongowski et al., 2006; Nadel et al., 2007; Veldman et al., 2010; Donati et al., 2013] and numerous case reports.

Gaps in knowledge and controversial study results constitute the major difficulties in establishing compelling recommendations for the treatment of SAPF. The longstanding concept that meningococcal infections are the principal cause of SAPF might need reconsideration in view of the broad introduction of meningococcal vaccination [Maat et al., 2007]. The evaluation of the importance of this factor is far from accomplished. The limited endurance of immunity achieved with the quadrivalent vaccine (Vu et al., 2006), and insufficient data on the epidemiological consequences of the recently introduced vaccines against meningococcal serotypes B (Martin and Snape, 2013), C and Y (Perry, 2013) pose difficulties in establishing a comprehensive overview. Suboptimal performance of certain protein products with regard to general sepsis outcomes (Martí-Carvajal et al., 2012; Nadel et al., 2007) has generated doubts as to their applicability and led to market withdrawal and corresponding changes in sepsis treatment guidelines [Dellinger et al., 2012]. Apart from a few experimental reports [Aoki et al., 2000], head-to-head comparisons of the efficacy of individual treatment modalities in SAPF have not been performed. Finally, systematic collection and evaluation of information on the epidemiology, causality, course, morbidity, comparative efficacy of therapeutic approaches, as well as effects of co-medication and outcomes of SAPF remains to be implemented.

## 7. Research questions and objectives

Clinical registries are valuable instruments for the continuous collection and assessment of information on the epidemiology and outcomes of rare diseases as well as for usage of drugs and medicinal products.

Registries are highly relevant pertaining to issues of quality assurance. They permit the evaluation of clinical benefit and general performance of the therapeutic approach/product under real-life conditions and large-scale application, and foster the usage of accumulated knowledge for the generation of performance benchmarks.

Unlike randomized controlled trials, registry data allow the identification of subcategories of patients, who display exceptionally pronounced or insufficient benefit of the treatment.

Ultimately, clinical registries are a powerful medium for the transfer of innovative therapy approaches into the clinical routine.

The present registry aims at

- Large-scale data accumulation and comprehensive evaluation of the incidence, causality and current treatment strategies of SAPF
- Comparative assessment of treatment strategies including or not including protein C supplementation
- Identification of patient subgroups of particular eligibility for Protein C treatment, as judged by established criteria of disease severity assessment
- Feedback of aggregated data to registry contributors, thus permitting quality management and standard updates
- Dissemination of data evaluation summaries and recommendations for the use of Protein C formulations in clinical routine
- Elaboration of a framework for SAPF treatment recommendations and guidelines

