## **8. Research methods**

### **8.1. Study design**

The registry comprises prospective, open-label data collection on the current state of incidence and management of SAPF, regardless of the etiopathogenic background. Using appropriate statistical techniques, specific emphasis will be laid on the comparison of outcomes in therapeutic approaches including or avoiding supplementation with Protein C formulations.

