#### 8.4. Data sources

Registry subjects will be identified by the participating centers. The recruitment will be primarily based on the concomitant presence of clinical signs of sepsis and *Purpura fulminans*. Clarification of the underlying etiopathogenesis will be performed *post hoc*, upon collection of additional clinical and laboratory data.

Data capture comprises assessment at baseline and at several intervals of 24 (initially) and 48 (subsequently) hours for an overall period of 7 days, while in ICU. A final appraisal of the patient's status will take place at the time point of discharge from the hospital.

The exposure to individual therapeutic agents will be deduced from doses and frequency of application during the period spent in ICU.

The influence of potential confounding variables and effect modifiers (e.g. concomitant anticoagulant medication, fluid resuscitation, renal replacement therapy etc.) will be extrapolated from the corresponding specific entries in the eCRF.

The outcome indicators have been previously validated and are routinely used.

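### Incidence of SAPF is a stated aim, but the protocol provides no denominator, no check on completeness of case capture and no incidence analysis, so that part of the aims cannot be met as written

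*Combined protocol and SAP*

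**What the plan says.** Incidence appears four times as an aim or a design purpose.

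- Section 4, first research objective: "Systematic acquisition, analysis and dissemination of information on incidence and prehospital/inhospital course of" purpura fulminans.
- Section 4, Design row: "Prospective multicenter registry derived from systematic data collection on the incidence and treatment of sepsis-associated" purpura fulminans.
- Section 7, first aim: "Large-scale data accumulation and comprehensive evaluation of the incidence, causality and current treatment strategies of SAPF".
- Section 8.1: "prospective, open-label data collection on the current state of incidence and management of SAPF".

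It is also part of the rationale. Section 4 states: "Most of the information on SAPF incidence and therapy has been obtained before 2004". Section 8.5 adds that the earlier incidence reports can hardly be carried over to the present, given meningococcal vaccination. The one incidence figure in the protocol is expressed per population (section 6): "The estimated incidence of the disease is 0.1 per 100,000 inhabitants".

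On case finding, the Centers row of section 4 gives "Approx. 30 participating centers in Germany, Austria, Ireland, UK, Italy, Spain, Netherlands (selected centers", and section 8.4 says: "Registry subjects will be identified by the participating centers". Inclusion requires consent under local rules (sections 4, 8.2 and 9). In the flowchart, baseline is ICU admission. Section 8.5 makes forecast recruitment depend on how many centres take part.

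**The concern.** An incidence estimate needs three things: a case count of known completeness, a population or admissions figure for the count to refer to, and a planned analysis that joins them. The protocol calls the old incidence information out of date and sets out to replace it, yet it supplies none of the three.

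This is more than detail left for later. Catchment and capture are not to be collected, so analysts could not recover them from the registry at the end. Section 11 foresees biannual reports, publications and treatment recommendations. Without a stated limitation, a count of enrolled patients could be presented, or read, as a current European incidence.

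**Working it through.** The study size is a recruitment forecast without a formula, and no incidence result is projected, so there is no planned figure to reproduce. The check has two parts.

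**1. Where an incidence measure would have to appear**

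| Place | What it contains | Incidence element |
|---|---|---|
| Section 4, Endpoints | mortality, morbidity scores, lesions, surgery, stay, laboratory values, organ support, pathogen, adverse events | none |
| Section 8.2, Flowchart | items for each enrolled patient only | none |
| Section 8.3, Variables | the same outcomes and laboratory values | none |
| Section 8.4, Data sources | centres identify subjects | no consecutive-enrolment rule, no record of cases not enrolled |
| Section 8.7, Data analysis | mortality regression, SOFA/PELOD changes, descriptive statistics for endpoints, group comparisons | none; incidence is not an endpoint, so the descriptive clause does not reach it |
| Section 8.8, Quality control | checks on data that were entered | no check for missed cases |
| Section 8.9, Limitations | mortality, lesion scoring, length of stay, biomarkers, co-medication | not mentioned |

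**2. What the count can and cannot give**

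Write incidence per year = n / (c × N), where n is enrolled cases per year, c the share of true cases that are enrolled, and N the population covered.

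- n: about 50 per year (section 4), or 50 to 70 in the first year and possibly 100 later (section 8.5). Over three years at 50 per year: 3 × 50 = 150.
- Per centre, with 30 centres: 50/30 = 1.7, 70/30 = 2.3 and 100/30 = 3.3 cases per year.
- c: not given and not to be collected.
- N: not given and not to be collected.

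With c and N both unknown, n fixes no value for incidence. If an external population figure P is used, and it is at least as large as the population really covered (P ≥ N), then because c ≤ 1, n/P ≤ n/(c × N). The result is at best a lower bound, and nothing in the data shows how far below the truth it lies.

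A confidence interval does not repair this. The exact Poisson 95% interval is 37.1 to 65.9 for 50 cases and 127.0 to 176.0 for 150 cases. It describes chance variation in the count and carries no information on c or N.

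**The case against.** Several points on the other side have force.

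- *The aims are compound.* Incidence is joined to clinical course, infectious agents, causality and treatment. The registry does collect pathogen, vaccination status and age, and much of the rationale concerns a shift in cause after vaccination. This stands: only the incidence component is unmet.
- *Incidence may be meant loosely, as case numbers.* Possibly, but the only incidence figure quoted is per inhabitants. If numbers are meant, the wording should say so.
- *Growth in numbers can be interpreted.* Section 9 keeps the centre of origin after anonymisation, so enrolled cases can be counted per centre and the effect of adding centres separated out. This stands, but it supplies neither catchment nor capture.
- *A log may exist elsewhere.* The eCRF and the Investigator Site File are not among the documents. A reader might infer that no site keeps a record of missed cases; that is not shown. What is shown is that this protocol does not provide for such a record and plans no analysis that would use one.
- *Incidence is not where the weight lies.* Section 8.1 puts specific emphasis on the Protein C comparison. Section 11 names etiology, clinical course and treatment as a major objective, and its open-ended list of outputs does not mention incidence. This stands and limits the consequence.

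**Conclusion.** The concern holds for one component of the aims. As written, the registry can describe enrolled SAPF cases at participating centres, in number, pathogen mix and characteristics, but cannot estimate incidence. This rests on the absence of any denominator, completeness check or incidence analysis from the sections tabulated above. It does not depend on any assumed rate. It deserves correction, but it does not touch the Protein C comparison.

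Three stronger readings are tempting and are not supported.

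- *A numerical size for the error.* Reading 0.1 per 100,000 as an annual rate (section 6 gives no time unit), 50 cases would correspond to 50 / (0.1/100,000) = 50 million inhabitants fully captured. A reader might take that as the registry's coverage, or build a range of rates around it. The protocol does not say what the centres cover, and section 8.5 names the same source among those that hardly permit extrapolation. Any such range would come from assumed inputs.
- *That chance variation is always the smaller problem.* This depends on the unknowns. If capture were 80% and catchment known (both assumptions), the correction would be 1/0.8 = 1.25, or +25%. That lies inside the Poisson limits for 50 cases, which run from 37.1/50 − 1 = −26% to 65.9/50 − 1 = +32%.
- *That the mortality result is biased by cases not enrolled.* The documents give no size or direction for this. It is a separate question, and this point makes no claim about it.

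**What to change.** Required, wording only:

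- In the aims and design statements of sections 4 (first objective and Design row), 7 (first aim) and 8.1, replace 'incidence' with 'number and characteristics of enrolled cases', adjusting the grammar in 8.1. References to incidence in the earlier literature can stay.
- Add to section 8.9: 'This protocol does not provide for collecting centre catchment or completeness of case capture; case counts refer to enrolled patients at participating centres and are not incidence.'

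The cost is a narrower claim. No data item, endpoint or analysis changes, and the correction can be made at any time before reporting.

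Optional, where local law allows: an anonymous aggregate count per centre of SAPF cases seen, enrolled and not enrolled, so that completeness of capture can be reported. The burden per site is small. Cases from before the count starts cannot be recovered, which matters because the first patient was planned for Q3 2015 and the last listed update is dated July 2019. The count would inform capture; without catchment it would still not give population incidence.

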## **8. Research methods**

### **8.1. Study design**

The registry comprises prospective, open-label data collection on the current state of incidence and management of SAPF, regardless of the etiopathogenic background. Using appropriate statistical techniques, specific emphasis will be laid on the comparison of outcomes in therapeutic approaches including or avoiding supplementation with Protein C formulations.

### **8.2. Setting**

The registry will include comprehensive records on diagnosis, morbidity and management of SAPF, supplied in the form of eCRFs by the participating centers over a period of three years.

The provision of informed consent by the patient or patient's legal guardian will be required for inclusion in accordance with local legal regulations.

The causal SAPF-inducing pathogen will be identified by microbiological examination.

The presence of Protein C deficiency and its contribution to the clinical manifestations of SAPF will be examined upon enrolment by determinations of Protein C concentration and activity, and subsequently documented in the eCRF. Changes in Protein C levels resulting from supplementation will be monitored as well.

The registry will also compare data on the efficacy of therapeutic approaches including or omitting Protein C supplementation.

A further aspect of specific interest is the stratification of outcomes by demographic (e.g. age, sex) and clinical criteria (e.g. morbidity at admission, causal pathogen), in order to identify subgroups of patients with above-average or marginal responsiveness to Protein C supplementation.

The contribution of supportive measures (e.g. assisted ventilation, renal replacement therapy, fluid resuscitation) and co-medication (e.g. vasopressors, corticosteroids, heparin etc.) will be evaluated as well.

